5.5 Study Evaluations

Screening

Pre-screening and screening procedures have been described above in pp. 27-33. See the Screening Checklists (Attachments L, RR, SS).

Study Measures

The primary study outcome is the Roland-Morris Disability Questionnaire (RMDQ). We will also collect several secondary outcomes as described below. All the main study outcomes as described below are patient-reported outcomes (PROs), except for Fitbit Zip-assessed daily step counts. A schedule of when each study measure will be administered is provided below in Table 5. The Study Measures are contained in the study assessments (Attachments, P, Q, R, and S).

- Roland-Morris Disability Questionnaire (RMDQ): The RMDQ is a back pain specific functional status questionnaire adapted from the Sickness Impact Profile (SIP).³ The RMDQ consists of 24 yes/no items, which represent common dysfunctions in daily activities experienced by participants with low back pain. A single unweighted score is derived by summing the 24 items, with higher scores indicating worse function with 0 (no disability) to 24 (maximum disability). The RMDQ was designed for paper administration, and is also well-suited for telephone use.
- *Fitbit Zip-Assessed Daily Step Counts:* Multiple recent studies have demonstrated the reliability and validity of the Fitbit Zip units as compared to actual observed step counts or legacy reference standard activity monitors such as the Modus Health StepWatch.⁴⁻⁶
- *Pain Numerical Rating Scale (NRS):* We will measure back pain using a 0-10 pain NRS (0=no pain and 10=worst pain imaginable) assessing average pain over the past week and pain "right now". Numerical rating scales of pain intensity are valid, reliable, and sensitive to detecting change in pain intensity after treatment.^{7,8} We will also ask participants to make a second report

of what they expect their NRS rating for back pain would be if they were not currently or recently taking medications for pain (analgesics).

- *PROMIS Short Form 10:* The NIH Task Force on Research Standards for Chronic Low Back Pain⁶² recommended using PROMIS Short Form items to assess the constructs of depression, anxiety, physical function, pain interference, fatigue, sleep disturbance, and satisfaction with participation in social roles. We will use the PROMIS Short Form 10, as recently recommended by an expert panel on the optimal core outcome measurement instruments for clinical trials in nonspecific low back pain (Chiarotto et al. *Core outcome measurement instruments for clinical trials in nonspecific low back pain*. Pain. 2018 Mar;159(3):481-495.)
- *Physical Activity*: Self-reported moderate and vigorous physical activities from the Behavioral Risk Factor and Surveillance System studies.
- *Global Perceived Effect:* This is a 7-point Likert scale describing change in disability since baseline and ranges from "much worse" to "much better".⁶³⁻⁶⁵ Participants will also assess their satisfaction with treatments received for LRFA, simulated LRFA, AcTIVE-CBT and TBSCE control.
- *Medications:* Patients will report medications they have taken for pain in the past 3 days.
- *Adverse Events:* Patients will report any adverse events they have experienced since the day of randomization/day of LRFA vs. simulated LRFA procedure.
- Ad hoc AE reporting: Participants will be given instructions at the time of informed consent to contact research staff by phone for AE reporting at any time, after the day of randomization/day of LRFA vs. simulated LRFA procedure.
- Bang Blinding Index: To assess success of participant blinding.

A schedule of study assessments is provided in **Table 5**. Over the follow-up period lasting at least 3 months, the following study assessments will be performed at VA Puget Sound, or conducted by telephone, as described below:

VISIT 1 (taking place at the time of the second MBBs) (60-70 mins duration)

Study assessments for Visit 1 will be conducted in person, coordinated to coincide with the timing of the participant's 2nd set of MBBs, *after* the 2nd set of MBBs. Where this is infeasible, some or all of the Visit 1 study assessment will be conducted over the phone, after the 2nd set of MBBs. Either in person or over the telephone, participants will answer questions (Attachment P – Survey Visit 1) including sociodemographic factors, the RMDQ, low back pain NRS, and medication use.

If Visit 1 is conducted in-person after the 2^{nd} set of MBBs, research staff will also make a brief followup phone call at least 2-5 days after the 2^{nd} set of MBBs, to ascertain the duration of low back pain relief after the 2^{nd} set of MBBs (Attachment L – Screening Checklist, question 21). This brief phone call will last <5 minutes. VISIT 2 (taking place on the same day as the LRFA or simulated LRFA with targeted steroid injections procedure, before the procedure) (20-30 mins duration)

Study assessments for Visit 2 will be conducted in person. Participants will answer questions (Attachment Q - Survey Visit 2) including the RMDQ, low back pain NRS, other pain questions, PROMIS SF-10, and medication use.

VISITS 3-4 (taking place 1 month and 2 months after your procedure (10-15 mins duration)

Table 5*	Screening & Baseline	Treatment	Optional
Study Phase			

Study assessments for Visit 3-4 will be conducted by telephone, unless a participant prefers to have these conducted in person at the Seattle campus. Participants will answer questions (Attachment R – Survey Visit 3_4) including the RMDQ, low back pain NRS, Global Perceived Effect and Satisfaction, medication use, and adverse event reporting.

VISIT 5 (taking place 3 months after your procedure (20-30 mins)

Study assessments for Visit 5 will be conducted by telephone, unless a participant prefers to have these conducted in person at the Seattle campus. Participants will answer questions (Attachment U – Survey Visit 5) including the RMDQ, low back pain NRS, other pain questions, PROMIS SF-10, Global Perceived Effect and Satisfaction, medication use, and adverse event reporting.

Visit Number/Name	1/Final Screen and Consent	2/ Baseline	3/ Month 1	4/ Month 2	5/ Month 3 (1º outcome)	Interim	6-14
Visit Timeline**	-1 to -4 wks.	0	1 mo.	2 mo.	3 mo.	3-6 mo.	Monthly
Length of Visit (min.)	60-70	20-30	10-15	10-15	15-20	10-15	10-15
Informed Consent	\checkmark						
Randomization		~					
LRFA vs. Simulated LRFA Procedure		~					
Sociodemographics	\checkmark						
Roland-Morris Disability Questionnaire and Physical Activity	~	~	~	~		-	~
Low Back Pain NRS	\checkmark	-	~	-	-		
Average Opioid Use	\checkmark	-		-	-		
Other Pain Questions		-			-		
PROMIS SF 10		-			-		
Global Perceived Effect and Satisfaction			~	~	A		~
Self-reported Medications		-	~	-	~	\checkmark	\checkmark
Adverse Event Reporting		\checkmark	~	~	~	\checkmark	~
Compensation	\$35	\$25	\$10	\$10	\$25	\$10	\$10

Interim Study Visit

If a participant elects a major change to their procedural or behavioral treatments for low back pain in the first 3 months after their procedure, we will offer an additional study visit that could be conducted over the phone, unless a participant prefers to have this assessment conducted in person at the Seattle campus. Participants will complete a questionnaire with several different sections, including the RMDQ, low back pain NRS, Global Perceived Effect and Satisfaction, medication use, and adverse event reporting.

Optional Study Assessments

After completing Visit 5, we will offer patients two choices about continued study participation and the manner of continued participation (blinded vs. unblinded). Participants may decide 'yes' or 'no' to either, neither, or both of these two choices listed:

 Participants can decide to be told which two of the 4 possible treatments they received (LRFA *or* targeted steroid injections to the facet nerves, and extended CBT *or* brief CBT) i.e. 'unblinding', or they may continue on *without* finding out which treatments they received (remaining blinded). If a participant decides to continue on in the study blinded, but wishes to learn this information at a later date, research staff will provide that participant with their treatment allocation information at any time until the conclusion of this study.

- 2) Participants may decide to continue on as part of this study (which would involve completing monthly telephone questionnaire by phone, for a period of 3-9 months longer after Visit 5), or decide to end participation in this study. If a participant were to continue as part of this study, the monthly questionnaires would be the same as what the participant completed by telephone during phone Visits 3-4, and would take between 10-15 minutes to complete. These optional assessments (Attachment S Survey Visits 6-14) are completely voluntary. If a participant initially decides to complete the optional assessments, but later opts to stop completing them, we will not offer the optional assessments again. Participants will be compensated for completing each optional assessment.
- 3) If a participant spontaneously offers expresses that they are ambivalent about the options discussed in #1 and #2 immediately above (unprompted by study staff), and requests more information, study staff will inform participants that remaining blinded to the treatments received for a longer period of time is more beneficial to meeting the study's goals, as is participants' continuing to complete the optional monthly assessments. Therefore, if a participant is truly ambivalent about the options discussed in #1 and #2 immediately above, remaining blinded and continuing with monthly assessments for as long as participants wish is the most useful course in terms of meeting the study's goals.
- 4) We will clarify that optional study visits will not take place after the formal end of the study, so some participants recruited late during the study will have fewer "optional" study visits that they can complete.

Participants will be informed that in this study, research staff will need to periodically look up participants' information in the electronic health record. This will be so for the duration of this study, a period that may last up to several years. This includes looking up such information from participants' health records after the 3-month follow-up period, irrespective of whether participants have decided to complete the optional telephone questionnaires. If a participant decides to withdraw from this study, however, and informs the research team not to access his/her health record after that time, we will not access that participant's health record after that time.

The analysis will examine treatment groups for baseline imbalances in covariates, understanding that our small sample size will limit the ability to adjust analyses in subsequent steps. We will then conduct an intent-to-treat analysis. Given that this is a preliminary study, the analysis will focus on effect sizes rather than statistical significance. Analyses will be conducted by research staff members biostatistician [name] and biostatistician [name] at the Seattle ERIC. We will examine for 'interactions' between the effect of LRFA (vs. control) and that of AcTIVE-CBT (vs. TBSCE control) on 3-month RMDQ scores, using a 2-way ANOVA. We will contrast the size of this estimate with that of the individual ('main effects') of LRFA vs. simulated LRFA (Figure 2; groups A+C vs. B+D) and AcTIVE-CBT vs. TBSCE control (groups A+B vs. C+D). If the size of interaction effect is small relative to the main effects, the main effects will inform estimation of the sample sizes needed for a future adequately powered RCT of LRFA vs. simulated LRFA or AcTIVE-CBT vs. control. Secondary comparisons of cell D vs. cell C, and cell D vs. cell B, would inform sample size estimation for a future RCT of combined treatment with LRFA + AcTIVE-CBT, compared to each of these treatments alone. If the size of interaction effect is large relative to the size of the main effects (making it inappropriate to study 'main effects'), power calculations for the future RCT will be based on the effect sizes yielded from comparisons of cell D vs. cell C, cell D vs. cell B, and cell D vs. cell A. We will follow the same approach for other study outcomes.

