Towards this end, this study will use a 2 x 2 factorial randomized controlled trial (RCT) design to investigate the individual and combined effects of **1**) **lumbar medial branch nerve radiofrequency ablation (LRFA)**, a commonly used procedural intervention to target low back pain severity, and **2**) **a telehealth tablet- and personal computer (PC)-based Activity Tracker-Informed Video-Enabled Cognitive Behavioral Therapy** program (which we call **"AcTIVE-CBT"**), a behavioral intervention designed primarily to target functional limitations both secondary to, and independent of, improvements in pain. AcTIVE-CBT is a modification of standard CBT delivered by video telehealth, which places a greater emphasis on increasing physical activity, and uses current activity tracker technology to support physical activity and an active lifestyle more broadly. For each of these 2 treatments, we will compare outcomes with another standard of care treatment that either poses 1) less risk, or 2) less inconvenience to the Veteran participant, but with potentially comparable or equivalent treatment benefits. The factorial **RCT design of this study will inform as to whether 'stacking' disparate CLBP treatments can result in greater treatment effects than that of each treatment alone.** This study will produce valid

VA Puget Sound IRB Protocol Template - Version 1.0: 04/2018

effect size estimates that will inform a definitive future large-scale multicenter RCT to determine the efficacy of LRFA, AcTIVE-CBT, or combined LRFA + AcTIVE-CBT, for Veterans with CLBP.

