3.0 Objectives

Study Aim: To estimate the individual and combined treatment effects of 1) LRFA (vs. simulated LRFA with targeted steroid injections to the facet nerves) and 2) AcTIVE-CBT (vs. a telephonebased self-directed CBT and education control) in up to 30 Veterans at 3-month follow-up. The primary outcome is participant-reported back-related functional limitations (mobility and ADLs) as measured by the Roland-Morris Disability Questionnaire at 3 months. Secondary outcomes include daily step counts, back pain intensity, reduction in opioid use, and quality of life.

Hypotheses: 1) Each individual treatment will result in improvements in back-related functional limitations and secondary outcomes compared to control, and 2) Combined treatment will produce greater treatment effects than each of the individual treatments alone.

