5.1 Study Design

We will conduct a 2 x 2 factorial pilot RCT to investigate the individual and combined effects of 1) lumbar radiofrequency ablation (LRFA) vs. simulated LRFA control with targeted steroid injections to the facet nerves, and 2) Activity Tracker-Informed Video-Enabled Cognitive Behavioral Therapy (AcTIVE-CBT) vs. TBSCE. For simplicity of language, henceforth in this protocol we frequently refer to simulated LRFA with targeted steroid injections to the facet nerves as 'simulated LRFA'. All treatments that will be allocated as part of this research are standard-of-care, "active" treatments expected to improve function and pain in those with CLBP. The study will recruit up to 30 Veterans, with the goal of having 20 Veterans with chronic low back pain (CLBP) who provide complete data for the main study outcome at 3-month follow-up postrandomization (the Roland-Morris Disability Questionnaire), with a minimum of 4 completers of the main 3month follow-up outcome in each of the 4 'cells' for treatment (see Figure 2). Participants would be blinded to whether they are receiving the study 'interventions' or 'controls', over the first 3 months of follow-up. Following the main period of data collection of 3 months of follow-up post-randomization, for those participants who wish to continue with the study, we will continue to collect observational data monthly thereafter for the duration of the funding period (up to 9 additional months); such data collection will continue with or without unblinding to participant group assignments per the randomization, according to what the participant decides. Unblinded participants may make subsequent treatment decisions as they wish, so optional assessments after the study period may be affected by unblinding and other changes in treatment and are not truly randomized comparisons. Participants who did not receive LRFA during the main 3-month period of follow-up may elect to pursue LRFA as part of normal clinical care, and those who receive TBSCE may elect to pursue standard video telehealth CBT (a typical 'extended' course of CBT).

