The randomization process involves:

- 1. Treatment assignments will be stored centrally electronically in a secure database at VAPSHCS. Envelopes containing the treatment assignments (hardcopies) will also be pre-generated.
- 2. We will utilize computer-generated permuted-block randomization to achieve roughly balanced groups. We will use random blocks that are not divulged to the research staff involved in recruitment in order to avoid bias in the recruitment process. Randomization will be stratified by MBB block responses (50-79% vs. ≥80%).
- 3. Reminder emails will be sent to the clinical assistant ([name]) and the 2nd interventional spine attending physician the day before the scheduled procedure to remind them that they will need to obtain the randomization allocation on the day of the procedure, prior to the procedure. The 2nd interventional spine attending physician is the second interventional spine attending physician-other than the treating spine provider, who will be in the room during LRFA or simulated LRFA and take part in these procedures. Similar emails will be sent on the morning of the procedure.
- 4. Prior to the lumbar procedure, the clinical assistant and the 2nd interventional spine attending physician will open the envelopes which reveal the procedural and behavioral treatment allocations. A non-blinded research staff member will be present to facilitate this and be aware of the treatment allocations. These assignments contained in the envelopes will direct the 2nd interventional spine attending physician whether to perform a standard LRFA or the simulated LRFA, and whether the participant will receive AcTIVE-CBT or TBSCE. A primary function of the clinical assistant is to make sure that the 2nd interventional spine attending physician knows and performs the allocated treatment on the day of the procedure.

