The AcTIVE-CBT treatment involves eight 60-minute treatment sessions spaced over 3 months, delivered via clinical video telehealth methods by clinical psychologists to Veterans in their homes. Psychologists will refer to Fitbit output during the initial evaluation and each treatment session, including reminders and tips about Fitbit use, evaluating step count homework, and tracking overall progress towards goals; the protocol for AcTIVE-CBT is provided as Attachment KK – AcTIVE-CBT Workbook. The TBSCE treatment involves an initial 60-minute telephone education session by a psychologist including education on CBT principles; the provision of an educational book for CBT self-management ('Managing Pain Before It Manages You' by Margaret A. Caudill PhD) and orientation to the workbook;⁴³ and a structured plan for weekly reading and homework using the workbook⁴³. The content of TBSCE interactions in the one initial 60-minute session is as per Attachment MM, but can be adapted to follow psychologists' typical practices for patients beginning CBT for pain who are interested in the treatment but are unable to continue with further sessions. In addition, the psychologist providing TBSCE will contact the participant at the approximate midpoint of the 3-month follow-up period to reinforce key concepts as needed, encourage continued participant-directed use of the plan for weekly reading and workbook use, and answer questions. The psychologist will also be available by phone to address any areas of concern or participant questions during follow-up. TBSCE represents a focused yet 'active' treatment beyond what is normally provided after LRFA. Around the time of the start of behavioral treatments for participants in both the AcTIVE-CBT and TBSCE arms, research staff will provide a written summary of certain data elements from Visit 0 and 1, reflecting the same type of information that would be obtained during an initial clinical evaluation for CBT. This written information will be shared in the form of Attachment NN ('Brief Summary Baseline Data' form). The purpose of this is to provide information to the therapist that will be useful in understanding the participant's baseline status and thus providing effective clinical care. These data elements will include report of pain intensity, number of pain locations, treatment expectancy, hours missed from work or volunteer activities, CLBP-related functional limitations, and past treatments for CLBP. The Brief Summary Baseline Data form (Attachment NN) will be generated by research staff and sent to the clinical therapist using the secure VHA Privacy Act/HIPAA Envelope or fax or encrypted email. If a fax is sent, once the fax receipt has been confirmed at the destination location (confirmed by the therapist), the original form will be destroyed via placement in a designated shredding bin (by the research staff member). If the therapist is located at Seattle campus, the research staff can come to the clinical area for a direct handoff of the Brief Summary Baseline Data form. Once the form is handed to the clinical therapist, the therapist can review this information and record whatever information they would normally do as per their usual clinical practice, in the medical record. The clinical therapist will then destroy the form via placement in a designated shredding bin, not retaining the record for future use, so as to limit potential risk for privacy issues.

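### Combined treatment versus each treatment 'alone' is not a contrast in this design: every cell receives a procedure and a CBT, so the active comparators should be named

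*Combined protocol and SAP*

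**What the plan says.** Three places describe the combination against single treatments.

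- Section 2.0 Introduction: the factorial design will show whether stacking "disparate CLBP treatments can result in greater treatment effects than that of each treatment alone".
- Section 3.0 Objectives, Hypothesis 2: "Combined treatment will produce greater treatment effects than each of the individual treatments alone".
- Section 5.6 Data Analysis: the secondary comparisons of cell D with cells C and B "would inform sample size estimation for a future RCT of combined treatment with LRFA + AcTIVE-CBT, compared to each of these treatments alone".

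Other places describe what participants receive.

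- Section 5.1, Randomization: the envelope tells the second physician "whether to perform a standard LRFA or the simulated LRFA, and whether the participant will receive AcTIVE-CBT or TBSCE". Each participant therefore gets one treatment of each kind.
- Section 5.1, opening paragraph: everything allocated is standard of care and active, "treatments expected to improve function and pain in those with CLBP".
- Section 5.1, technique of the simulated procedure: a corticosteroid is injected at each targeted nerve.
- Section 5.1, description of the CBT treatments: TBSCE is a focused but active "treatment beyond what is normally provided after LRFA".

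The Study Aim in section 3.0 does name the comparators: simulated LRFA with steroid injections for one factor, the TBSCE control for the other.

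**The concern.** The rationale in section 2.0 is that joining a procedural to a behavioural treatment should give larger effects than either kind by itself. If all four cells already join the two kinds, no cell shows what LRFA does without CBT, or what AcTIVE-CBT does without a procedure. The trial can then show whether a more intensive version of one component adds to the other. It cannot show whether combining the two kinds of treatment beats giving one.

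Two things are at stake. The first is interpretation: a small difference between LRFA + AcTIVE-CBT and LRFA + TBSCE may only mean that brief CBT does about as well as extended CBT, a possibility that section 2.0 raises itself. The second is the pilot's main product. Section 5.6 gives its purpose as supplying effect sizes and variability for a definitive trial. An effect size labelled as combined versus alone could be carried into a trial whose comparator really is one treatment alone.

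**Working it through.** **Cells by content.** Section 5.6 uses the letters of Figure 2, which is not shown in the text available. Its sentence on combined treatment needs D to be the combined cell. With the groupings given there (A+C against B+D for the procedure, A+B against C+D for the CBT), the cells are then:

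| Cell | Procedure | CBT |
|---|---|---|
| A | simulated LRFA with steroid | TBSCE |
| B | LRFA | TBSCE |
| C | simulated LRFA with steroid | AcTIVE-CBT |
| D | LRFA | AcTIVE-CBT |

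No row has an empty column.

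**What the contrasts estimate.**

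- D minus B: AcTIVE-CBT minus TBSCE, given LRFA.
- D minus C: LRFA as delivered minus simulated LRFA with steroid, given AcTIVE-CBT.

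**When they would equal combined versus alone.** Among patients given LRFA, let a be the gain from adding AcTIVE-CBT and b the gain from adding TBSCE, each against no CBT. Combined versus LRFA alone is a. D minus B is a - b. The two agree only if b = 0. Against b = 0, section 2.0 allows that the comparators may do as well as the study treatments, section 5.1 expects all of them to improve function and pain, and section 5.1 places TBSCE above usual care after LRFA. The same argument applies to D minus C with the steroid procedure. There, section 5.1 also reports that randomised trials show no significant difference in functional limitations between LRFA and targeted steroid injections.

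**The plan's own figures.** Section 5.6 gives no alpha, power, effect size or SD for any contrast. Its recruitment arithmetic reproduces: 30 - 10 = 20 completers, and 20 / 4 = 5 per cell if balanced, with a stated minimum of 4.

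**Effect on a future sample size (illustration).** Write b = f × a, where f is the share of the AcTIVE-CBT gain that TBSCE also gives. The documents give no value for f. Then D minus B = (1 - f) × a. Because the required N is proportional to 1/effect², N for a true alone comparator, planned from D minus B, is multiplied by 1/(1 - f)².

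Assume also a = 0.5 SD, two-sided alpha 0.05 and 80% power, so that n per arm = 2 × (1.960 + 0.842)² / d²:

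| f | Apparent effect d | n per arm | Ratio 1/(1 - f)² |
|---|---|---|---|
| 0 | 0.5 SD | 63 | 1 |
| 0.25 | 0.375 SD | 112 | 1.8 |
| 0.5 | 0.25 SD | 252 | 4 |

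**Precision, for scale.** With a pooled variance from four cells of n, the 95% half-width of D minus B or D minus C is t(0.975, 4(n - 1)) × √(2/n). At n = 5 this is 2.120 × 0.632 = 1.34 SD. At n = 4 it is 2.179 × 0.707 = 1.54 SD.

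**The case against.** The best defence is that alone is ordinary factorial shorthand for the other factor at its control level. The Study Aim directly before Hypothesis 2 names both controls, Hypothesis 1 speaks of comparison with control, and section 2.0 introduces the active comparators just before the stacking sentence. Read that way, D versus B and D versus C are the right simple effects. This reading is plausible, but the text never defines the word so. It also does not rescue the stacking claim, because the control cells already stack a procedure on a CBT. Nor does section 5.6 say that a future trial of the combination would keep these controls.

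A reader might infer four stronger things that the documents do not support.

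- *The factorial comparison is invalid.* It is not. Allocation is randomised, and the simple effects are sound against the comparators given.
- *All planning for the next trial rests on the mislabelled contrasts.* If the interaction is small, main effects size a trial of LRFA against simulated LRFA or of AcTIVE-CBT against control, and the comparisons labelled alone are secondary. If it is large, the contrasts are named by cell and include D versus A.
- *The next trial will be several-fold too large.* That needs a value of f that the documents do not give, and a future trial with a no-CBT or no-procedure arm, which they do not propose. The half-widths above also show that sampling error in these contrasts would be large whatever the label.
- *D versus C isolates lesioning against steroid injection.* Section 5.1, LRFA Technique, lets providers use local corticosteroid with LRFA, so the contrast is LRFA as delivered against the simulated procedure.

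The active comparators were also a deliberate choice with a stated rationale. That choice is not at issue; the description of what it can show is.

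**Conclusion.** The point stands as a fault of estimand and labelling. The design does not contain the comparison claimed in section 2.0, in Hypothesis 2 and in the secondary-comparison sentence of section 5.6. What it contains are increments over two active regimens, LRFA + TBSCE and simulated LRFA with steroid injection + AcTIVE-CBT. These match combined versus alone only if the controls add nothing, contrary to what the protocol says of them.

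The size of the consequence is not determined by the documents. The direction shown, an understated increment and an oversized trial, assumes that the controls give some benefit and that a later trial uses a true single-treatment comparator. If the later trial keeps the same controls, these contrasts are the right inputs.

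**What to change.** 1. In 2.0, 3.0 and 5.6, replace the references to each treatment alone with the comparators given: LRFA + TBSCE, and simulated LRFA with steroid injection + AcTIVE-CBT.
2. Restate Hypothesis 2 as two increments: AcTIVE-CBT over TBSCE in patients given LRFA, and LRFA as delivered over simulated LRFA with steroid injection in patients given AcTIVE-CBT.
3. In 5.6, state that these effect sizes may size a future trial only if it keeps the same active controls, and that they do not estimate combined treatment against LRFA without CBT or against AcTIVE-CBT without a procedure. Apply this to the large-interaction branch too, since it uses the same contrasts.
4. In 5.6, name the cells by content as well as by letter.

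The cost is a protocol wording change and a narrower claim than the introduction makes. It adds no participants, visits or procedures.
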